8.3 Descriptive Parameters

TEWL (Trans-epidermal water loss) measurements and Chromometer readings will be carried out at Day 1, Day 3, Day 4 and Day 5. On each day, TEWL (Trans-epidermal water loss) measurements and Chromometer readings will be collected for each treatment region.

8.4 Baseline Values

For analyses based on grades, each treatment region will be assigned its own baseline value. The baseline values for regions under Treatment Regimen 1 and 2 will be the values collected at Day 3.

The baseline values for TEWL measurements and Chromometer readings will be the assessments collected on Day 1.

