### 2.2. Secondary Objectives

- Proportion (%) of subjects who, with pre-treatment, have a  $\geq 1$  grade reduction of the cutaneous reaction to nickel sulfate in at least one patch region at 48 hours
- Proportion (%) of subjects with a  $\geq 1$  grade reduction of the cutaneous reaction to nickel sulfate in at least one patch region after treatment
- Proportion (%) of subjects that have a  $\geq 1$  grade reduction of the cutaneous reaction to nickel sulfate in at least one patch region at Days 2, 3, 4, or 5
- Safety and tolerability of the injection based on AEs, physical examinations, and vital signs

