### **3.2. Duration Of Time On Study**

Study subjects will be screened (Visit 1) for eligibility within 21 days prior to receiving study drug. The baseline nickel allergy patch test must be administered no less than 14 days after the screening nickel allergy test.

- Visit 2 (Day 1) will consist of the nickel patch test (Treatment regimen 1) and pre-treatment and then the nickel patch test (Treatment regimen 2)
- Visit 3 (Day 3) is the day of first treatment dose and conducted 2 days (no less than 48 hours) after V2
- Visits 4-7 (Days 4-7) are dose days
- Visit 8 will be conducted seven days after the last dose

Therefore, the anticipated duration of time on study for a given subject, from Screening to completion of the study is up to 35 days.

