### 5.1.2. Baseline (Visit 2; Day 1)

#### Subject Arrival at Site:

As shown in [Appendix A](#), Study Schedule of Events, the following activities are to be completed during this visit.

- Confirm subject meets inclusion and exclusion criteria
- Assign Randomization Number (at Baseline visit only)
- Review concomitant medication use
- Vital signs collection (BP, heart rate, respiration rate)
- Pregnancy test (only for females of child bearing potential)
- Targeted physical exam
- Physical examination of the administration site
- Perform baseline TEWL, Chromometer, digital photography assessments
- Mark the upper back into 2 rows of 4 areas each (see [Figure 1](#))
- Treatment Regimen 1 - Apply the nickel sulfate patches (see [Appendix C](#)) at the concentration that caused no greater than a ++ cutaneous reaction (ICDRG scoring scale, see [Appendix B](#))
- Treatment Regimen 2 - Administer the intra-dermal injection of rHuPH20 or placebo. Exactly 10 minutes after the injection, apply a single row of four patches (1%, 2.5%, or 5% nickel sulfate patches; determined for each subject during the Screening period) over the center of the intra-dermal injection
- Assess Adverse Events (AE's)
- Assess injection site

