cutaneous reaction an ID syringe push bolus injection of either rHuPH20 or placebo control. Each injection will be administered once daily for 5 days. Prior to each daily injection, subjects will be evaluated for efficacy, safety, and tolerability. A final evaluation will be conducted 7 days after the last dose of study treatment.

Treatment Regimen 2 (TR2-5 – TR2-8):

This regimen will assess the prevention and treatment of contact allergy to nickel sulfate. Each subject will receive in the center of each lower space on the back, either an ID syringe push bolus injection of rHuPH20 or placebo control. Exactly 10 minutes after the injection, a single row of four patches (1, 2.5, or 5% nickel sulfate patches; determined for each subject during the Screening period) will be placed over the center of the ID injection. After 48 hours, the patches will be removed and an assessment will be made of the reaction site as per the ICDRG scoring system. The subject will receive an ID injection of the same study drug from pre-treatment in the center of the cutaneous reaction once daily for 5 days. Subjects will be evaluated for efficacy, safety, and tolerability, on a daily basis. A final evaluation will be conducted 7 days after the last dose of study treatment.

For a given subject, the anticipated duration of time on study is up to 35 days, which include Visit 1 (screening, within 21 days prior to receiving study drug), Visit 2 (Day 1), Visit 3 (Day 3), Visits 4 – 7 (Day 4 – 7) and Visit 8 (Day 14).

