8.2 Secondary Variables

Analyses of the secondary endpoints will be based on the grades shown in ICDRG table in Section 8.1.

For Treatment Regimen 1 and 2, proportion of subjects that have a ≥ 1 grade reduction of the cutaneous reaction to nickel sulfate in at least one patch region after treatment.

For Treatment Regimen 2, proportion of subjects that have a ≥ 1 grade reduction of the cutaneous reaction to nickel sulfate in at least one patch region at 48 hours (Day 3) will be assessed.

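### The Regimen 2 48-hour grade reduction is measured from Day 3 to Day 3, so under the SAP's only stated baseline it is zero for every subject

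*SAP*

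**What the plan says.** **The endpoint.** SAP 8.2 states: "Analyses of the secondary endpoints will be based on the grades shown in ICDRG table in Section 8.1". For Regimen 2 it then defines the share of subjects whose reaction falls by at least one grade "in at least one patch region at 48 hours (Day 3) will be assessed". Protocol 2.2 lists the same quantity for pre-treated sites, a "grade reduction of the cutaneous reaction to nickel sulfate in at least one patch region at 48 hours". Neither place says what the reduction is measured from.

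**The baseline.** SAP 8.4 states: "For analyses based on grades, each treatment region will be assigned its own baseline value". It continues: "The baseline values for regions under Treatment Regimen 1 and 2 will be the values collected at Day 3". SAP 8.1 plans grades only from Day 3 onward (Days 3 to 7 and Day 14).

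**The timing of injections.** Regimen 1 sites are first injected on Day 3, after patch removal. Regimen 2 sites are injected on Day 1. Protocol 5.1.2 lists for that visit: "Treatment Regimen 2 - Administer the intra-dermal injection of rHuPH20 or placebo". SAP 3 gives the order: "Exactly 10 minutes after the injection, a single row of four patches" is applied over the injection. Protocol 3.2 nevertheless says "Visit 3 (Day 3) is the day of first treatment dose".

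**The analysis.** SAP 9.1 sends the grade-reduction proportions to a qualitative medical review of displayed scores. It labels the first display point Baseline for both regimens. In its Regimen 2 paragraph it also treats a Day 3 maximum as having come before treatment.

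**The concern.** A baseline for a treatment effect has to come before the treatment. Day 3 does so in Regimen 1. In Regimen 2 it is the first reading after an injection given about 48 hours earlier, so it is an outcome. SAP 10.1 is consistent with this: it reports Regimen 2 injection-site events from Day 1.

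The 48-hour proportion is the secondary endpoint that addresses the first study hypothesis (Protocol 8, SAP 9), that pre-treatment lowers the severity of the reaction. If the stated baseline is applied, the endpoint cannot show an effect of either injection. If it is not applied, the endpoint has no reference, and someone will have to choose one, possibly while looking at displays that label each site as active or placebo.

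The separate Regimen 2 endpoint after treatment has a lesser version of the problem. Its starting grade may already have been lowered by the Day 1 injection, and a low start leaves no room for a one-grade fall.

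**Working it through.** The plan states no figure for this endpoint, and its sample size of 20 comes without inputs, so there is nothing to reproduce. The check applies the SAP's own rules.

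**Inputs.** Grades are 0, 1/2, 1, 2 and 3, and IR has no grade (SAP 8.1). Each subject has four Regimen 2 regions, two rHuPH20 and two placebo (Protocol 3.1, SAP 3). The baseline is the region's own Day 3 grade (SAP 8.4). A responder has a reduction of at least 1 in at least one region (SAP 8.2). Missing values are not imputed (SAP 8.5).

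**Step 1, the 48-hour endpoint.** Reduction = baseline − grade at 48 hours = Day 3 − Day 3 = 0 for every grade. There are 5⁴ = 625 grade patterns on four regions, and 0 of them contain a reduction of at least 1. At the planned 20 evaluable subjects the result is 0/20. IR or missing regions give an undefined change, not a reduction.

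**Step 2, is another reference available?** Three candidates can be constructed, but neither document names any of them as the reference for a reduction. The counts below are numbers of patterns, not probabilities.

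| Reference | Day 3 result that counts | Patterns that count |
|---|---|---|
| Own Day 3 grade (SAP 8.4) | none | 0 of 625 |
| Day 1 intact skin, taken as 0 | none | 0 of 625 |
| Screening grade + (1) | 0 | 25 − 4² = 9 of 25 per injection type |
| Screening grade ++ (2) | 0, 1/2 or 1 | 25 − 2² = 21 of 25 per injection type |
| Lower placebo grade | an rHuPH20 region at least 1 below it | 132 of 625 |
| Mean placebo grade | same | 270 of 625 |
| Higher placebo grade | same | 408 of 625 |

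The answer depends heavily on the choice, so the choice has to be made in advance.

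**Step 3, the endpoint after treatment.** The largest possible later fall equals the Day 3 grade. A region at 0 or 1/2 on Day 3 (2 of the 5 grades) can never respond.

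- Both regions of one injection type below grade 1: 2 × 2 = 4 of 25 patterns.
- Exactly one below grade 1: 2 × 2 × 3 = 12 of 25. The subject can still respond through the other region.
- All four regions below grade 1: 2⁴ = 16 of 625.

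**Step 4, a worked subject.** Take screening ++, both rHuPH20 regions negative and both placebo regions ++ on Day 3, and all four negative by Day 14.

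- As written, the 48-hour reduction is 0 in all four regions. After treatment, if reported by injection type, rHuPH20 is a non-responder and placebo a responder (2 − 0 = 2). Pooled over regions, the subject responds.
- Compared directly, the Day 3 difference is 0 − 2 = −2, in favour of rHuPH20. With the screening grade as reference, rHuPH20 responds (2 − 0 = 2) and placebo does not (2 − 2 = 0).

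**Step 5, combining two regions.** A direct Day 3 comparison needs a rule for the two regions of each injection type. The mean rule is symmetric: 280 patterns lower, 65 equal and 280 higher. Table 6.1 uses the single most severe patch instead. The two rules give a different sign in 148 of 625 patterns: 20 equal only by mean, 120 equal only by most severe, and 8 in opposite directions.

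**The case against.** Neither document says the reduction is from baseline. The hypothesis is framed against placebo, and the primary analysis is a within-subject comparison of injection types, so the 48-hour reduction could be read as relative to the placebo sites. That reading does not rescue the endpoint. It conflicts with SAP 8.4, which gives every region its own baseline, and it still lacks a rule for two placebo regions.

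The arguments about harm carry more weight, and these stand:

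- Appendix A lists no table for any grade-reduction proportion, so no programmed output would print a zero. The figure would come from the medical review.
- SAP 4 already requires analyses made after unblinding to be identified as post hoc.
- SAP 8.1 includes the Regimen 2 grades at Day 3, and Figure 1 and Listing 8 show them by site and injection type.
- The documents separate pre-treatment on Day 1 from treatment starting on Day 3. In that vocabulary Day 3 is a possible start for the endpoint after treatment, and the SAP 9.1 wording is partly a matter of terms.
- The pattern counts weight all grades equally and say nothing about how often each occurs.

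It is also fair that one sentence in SAP 8.2 naming a reference would cure the zero. It would leave SAP 8.4 and 9.1 describing a post-injection reading as baseline.

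**Conclusion.** The concern holds. The stated rule makes the Regimen 2 48-hour reduction zero for every grade, in 0 of 625 patterns a responder, regardless of any true effect. This assumes that SAP 8.4 governs the endpoint, as its wording on grade-based analyses implies. If it does not, the reference is undefined and the same repair is needed.

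The consequence is contained: one secondary, descriptive proportion, with the raw Day 3 grades intact. What remains is the risk of a reported zero, or of a proportion built on a reference picked after treatment labels are visible. The Regimen 2 proportion after treatment is a lesser limitation. Given by injection type, it can favour placebo if prevention is near complete, but SAP 8.2 does not say whether it will be split that way, and the size of any bias cannot be derived from the documents. This should be fixed before unblinding.

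**What to change.** Before unblinding:

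1. **SAP 8.4 and 9.1.** Limit the Day 3 grade baseline to Regimen 1. For Regimen 2, call Day 3 the first post-injection assessment, used as a reference only under item 4. In SAP 9.1, head the first Regimen 2 column Day 3 instead of Baseline, and reword the sentence on a maximum before treatment to say that it fell on Day 3. Add a footnote to Table 6.1 that Day 3 is the first post-injection reading.
2. **Direct comparison at 48 hours.** Report the within-subject rHuPH20 minus placebo difference in Day 3 grade, using the mean of the scored regions of each injection type. If one region is IR or missing, use the other. If both are, leave the subject out for that visit and report the number. Show counts lower, equal and higher and the median difference, for the Evaluable and ITT populations.
3. **The protocol's 48-hour proportion.** Keep it, in SAP 8.2, with the subject's screening 48-hour grade at the assigned concentration as reference. Report it by injection type and separately for + and ++ subjects. An IR region is not a reduction. If both regions of a type are IR or missing, omit the subject for that type.
4. **After treatment.** Label any Regimen 2 proportion as change from Day 3, and give beside it, by injection type, the number of regions below grade 1 on Day 3.

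The cost is wording in SAP 8.2, 8.4 and 9.1, one footnote and one small descriptive table. The Day 3 to Day 14 grades (Listing 8) and screening grades by concentration (Listing 13) are already collected, so no visits or subjects are added. The drawback is that the screening grade comes from another site and date, so only the rHuPH20 versus placebo contrast can be interpreted. A + subject counts only at a negative reading, and a ++ subject at negative, doubtful or +, so the two strata should not be pooled.

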8.5 Handling Missing Data

No missing values will be imputed.

8.6 Interim Analyses

No interim analyses are planned for this study.

9. STUDY ANALYSIS

The hypothesis for this study is that 1) pre-treatment or rHuPH20 prior to nickel allergy testing will decrease the severity of the allergic skin reaction as compared to placebo control and 2) rHuPH20 will decrease the severity of nickel contact dermatitis as compared to control. The null hypothesis is that rHuPH20 will not be different than what will be observed from placebo control.

Figures, listings and descriptive statistics will be used to summarize all efficacy variables. No formal statistical comparisons between treatments are planned.

9.1 Statistical Analyses

The primary analysis is the pair-wise intra-subject comparison of endpoint parameters for the injections with and without rHuPH20. The secondary analysis covers safety and other endpoint parameters (see Section 10).

ICDRG scores will be shown for Treatment Regimen 1 and Treatment Regimen 2 by injection types (rHuPH20 or Placebo) at Baseline, Day 4, Day 5, Day 6, Day 7 and Day 14. ICDRG scores will be reported by subject using figures (Figure 1) and listings (Listing 8).

A qualitative medical review of the ICDRG scores will be used to investigate:

- Possible treatment effect of rHuPH20 or placebo control injection on the exposure to topical nickel allergen.
- Proportion of subjects that have a ≥ 1 grade reduction in at least one patch region.

At the conclusion of the study, findings from the medical review will be summarized in the clinical study report.

For Treatment Regimen 2, the day of maximal ICDRG Score will be used to assess the possible effect each injection type has on the onset of reaction to topical nickel allergen. The day of maximal ICDRG Score will be summarized for each injection type using counts and percentages (Table 6.1/6.2). Possible days of maximal ICDRG Score include

the following: Day 4, Day 5, Day 6, Day 7, and Day 14. If the maximal ICDRG Score for an injection type occurred prior to treatment, the subject will be reported as never having had an ICDRG Score more severe than Day 3 for summary purposes.

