## 8. DATA ANALYSIS AND STATISTICAL CONSIDERATIONS

### Primary and Secondary Analysis

The primary analysis is the pair-wise intra-subject comparison of endpoint parameters for the injections with and without rHuPH20. The primary analysis is the observer's assessment of the nickel sulfate allergen reaction site. The ICDRG scoring system will be used to conduct this assessment, which is either + (Weak [non-vesicular] positive reaction: Erythema, infiltration, possibly papules) or ++ (Strong [vesicular] positive reaction: Erythema, infiltration, papules, vesicles). Secondary analysis of the study is the comparison of safety and other endpoint parameters for the SC administration between rHuPH20 and placebo control.

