### Dataset for Analysis

The primary analysis data set for this study will consist of all evaluable subjects. An evaluable subject is one who has completed dosing (or prematurely discontinued the administration due to a toxicity) and has undergone sufficient assessments to allow an assessment of the tolerability of the administration. A secondary analysis data set will consist of all intent-to treat subjects (ITT) (i.e., all subjects enrolled, defined as subjects assigned a subject identification number at the time of study enrollment in anticipation of receiving a dose of study drug). The safety analysis data set is all subjects exposed to rHuPH20 or placebo control.

The hypothesis is that 1) pre-treatment of rHuPH20 prior to nickel allergy testing will decrease the severity of the allergic skin reaction as compared to placebo control and 2) rHuPH20 will decrease the severity of nickel contact dermatitis as compared to control. The null hypothesis for this study is that rHuPH20 will not be different than what will be observed from placebo control. The alternative hypothesis is that rHuPH20 will be better than placebo control.

The sample size of 20 evaluable subjects is intended to provide a sufficient sample size to allow for a meaningful comparison between rHuPH20 and placebo control.

All data collected, including demographics, baseline information, contact dermatitis scoring, safety data, will be summarized by treatment group. Descriptive statistics including the number of observations (N), mean, standard deviation, median, and range will be presented for the continuous variables. Frequency and percentage will be presented for categorical variables. Figures of the individual measurements over time by subject and means by treatment group may also be provided.

Descriptive statistics will be used to summarize all efficacy variables. No formal statistical comparisons between treatments are planned.

All safety data will be examined, including AEs, physical examination findings, and vital signs. The incidence of subjects with AEs will be tabulated by MedDRA System Organ Class (SOC) and Preferred Term, seriousness, severity grade, relatedness to study drug, and localization to infusion site. Descriptive statistics will be used to summarize all safety variables.

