4. GENERAL ANALYSIS CONSIDERATIONS

The statistical analyses will be reported using summary tables, figures, and data listings. Descriptive statistics will be used to summarize all efficacy variables. No formal statistical comparisons between treatments are planned. Continuous variables will be summarized with means, standard deviations, medians, minimums, and maximums. Categorical variables will be summarized by counts and by percentage of subjects in corresponding categories.

Individual subject data obtained from the case report forms (CRFs), local lab and any derived data will be presented by subject in data listings.

The analyses described in this plan are considered a priori, in that they have been defined prior to database lock and prior to breaking the blind. Any analyses performed subsequent to breaking the blind will be considered post-hoc. Post-hoc analyses will be identified in the CSR.

All analyses and tabulations will be performed using SAS® Version 9.1 on a PC platform. Tables and listings will be presented in RTF format. Figures will be presented in PDF format. Upon completion, all SAS® programs will be validated by an independent programmer. In addition, all program output will undergo a senior level statistical review. The validation process will be used to confirm that statistically valid methods have been implemented and that all data manipulations and calculations are accurate. Checks will be made to ensure accuracy, consistency with this plan, consistency within tables, and consistency between tables and corresponding data listings. Upon completion of validation and quality review procedures, all documentation will be collected and filed by the project statistician or designee.

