5. ANALYSIS POPULATIONS

The ITT population will include all enrolled subjects (all subjects who got a subject identification number assigned at the time of study enrollment in anticipation of receiving a dose of study drug).

The Safety population will include all subjects who receive at least one dose of study drug.

The Evaluable population will include all evaluable subjects. An evaluable subject is one who has completed dosing (or prematurely discontinued the administration due to a toxicity) and has undergone sufficient assessments to allow an assessment of the tolerability of the administration.

A subject is considered to have undergone sufficient assessments to allow an assessment of the tolerability of the administration if the subject has at least one ICDRG score reported on Day 4 or later.

A subject is considered to have prematurely discontinued the administration due to toxicity if the subject has Adverse Event checked as the reason for not completing the study on the Study Completion/Termination CRF page, and has Drug Withdrawn as the action taken with study drug checked on the Adverse Event CRF page.

Efficacy analyses will be run on the Evaluable population and the ITT (Intent-to-Treat) population. Analyses run on the Evaluable population will be considered the primary analyses.

Safety analyses will be run on the Safety population.

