8.1 Primary Variables

The primary efficacy endpoint will be based on the International Contact Dermatitis Research Group (ICDRG) Scoring Scale. Using the ICDRG Scoring Scale, each score will be assigned a Sponsor-defined “grade”. Scores with stronger reactions will be assigned grades with higher values with a maximum grade of 3; scores with weaker reactions will receive lower values with a minimum grade of 0. Grade assignments based on the ICDRG Scoring Scale are shown in the table below.

International Contact Dermatitis Research Group (ICDRG) Scoring Scale

Grade	Score	Interpretation
0	-	Negative reaction
1/2	?	Doubtful reaction; faint macular erythema only
1	+	Weak (nonvesicular) positive reaction; erythema, infiltration, papules, vesicles
2	++	Strong (vesicular) positive reaction; erythema, infiltration, papules, vesicles
3	+++	Extreme positive reaction; bullous reaction
NA	IR	Irritant reaction of different types

Treatment effect of rHuPH20 or placebo control injection on the exposure to topical nickel allergen will be assessed using ICDRG grades for Treatment Regimens 1 and 2 at Day 3 through Day 7 and Day 14.

Regimen 2 only: For each subject, the day of maximal ICDRG score will be determined for each injection type (rHuPH20 and Placebo). The maximal ICDRG score will be the highest score reported for each subject. If the maximal ICDRG score for a particular subject is reported more than one time, the first instance will be used to determine the day when the maximal ICDRG score was reached.

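### The declared primary comparison, rHuPH20 against placebo within subject, has no defined summary: ICDRG grades go to a qualitative medical review and no planned table summarises them

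*SAP*

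**What the plan says.** Protocol Section 8 states: "The primary analysis is the pair-wise intra-subject comparison of endpoint parameters for the injections with and without rHuPH20". SAP 9.1 repeats the sentence. SAP 8.1 converts ICDRG scores to grades (0, 1/2, 1, 2, 3, with an irritant reaction set to NA) and says that the treatment effect "will be assessed using ICDRG grades for Treatment Regimens 1 and 2 at Day 3 through Day 7 and Day 14".

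On summaries, SAP 9 promises: "Figures, listings and descriptive statistics will be used to summarize all efficacy variables". SAP 4 adds: "Continuous variables will be summarized with means, standard deviations, medians, minimums, and maximums". Protocol Section 8 says: "All data collected, including demographics, baseline information, contact dermatitis scoring, safety data, will be summarized by treatment group". SAP 5 adds: "Efficacy analyses will be run on the Evaluable population and the ITT (Intent-to-Treat) population".

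For the ICDRG data themselves, SAP 9.1 provides by-subject displays (Figure 1 and Listing 8) and then says: "A qualitative medical review of the ICDRG scores will be used to investigate" two things, namely a possible treatment effect and the proportion of subjects with a reduction of at least 1 grade. SAP 8.2 describes the latter for both regimens as a "grade reduction of the cutaneous reaction to nickel sulfate in at least one patch region after treatment", with a further 48-hour (Day 3) version for Regimen 2. SAP 8.4 makes Day 3 the grade baseline for every patch in both regimens. Both documents say that no formal comparison between treatments is planned.

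**The concern.** A paired comparison needs a contrast: what is subtracted from what, how the two patches on the same drug are combined, and what is reported. The SAP gives none of these for grades. Followed as laid out, the plan would answer its primary question by medical judgement, and its shells would state neither the size nor the spread of the within-subject difference in either regimen.

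Timing adds to this. SAP 4 treats any analysis performed after unblinding as post hoc unless the plan has already defined it. Figure 1 and Listing 8 print the treatment letter beside each score, and the SAP does not say that the medical review is blinded. A paired number first thought of at that stage would be post hoc by the SAP's own rule.

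Both study hypotheses (SAP 9) concern severity: at 48 hours after pre-treatment, and of established dermatitis. Neither gets a severity table.

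**Working it through.** The plan has no figure of its own to reproduce here. The sample size of 20 evaluable subjects is given without an effect size, SD, error rate or power. The check therefore sets the promise against the planned outputs.

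**1. Tables.** SAP Appendix A lists 15 tables. Tables 1 to 5 cover disposition, demographics, history and screening laboratory data. Table 6 is the day of maximal ICDRG score. Tables 7 to 15 cover adverse events, vital signs, physical examination and concomitant medication. One of 15 concerns efficacy, and none summarises grades.

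**2. What Table 6 can show.** It covers Regimen 2 only, with a column of counts for each injection type. Each subject contributes one entry per column and the columns are not cross-classified, so the pairing is not carried into the table. It also records when the maximum occurred, not how high it was. Take a subject whose rHuPH20 patches peak at + (grade 1) on Day 3 and whose placebo patches peak at +++ (grade 3) on Day 3. Both entries fall in the row for scores that never exceeded Day 3. The paired grade difference at Day 3 would be 1 − 3 = −2 grades, and Table 6 shows nothing of it.

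**3. Regimen 1.** No table covers it. Its only ICDRG outputs are the per-subject map and the listings.

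**4. The reduction proportion.** The grade (SAP 8.1), the threshold (SAP 8.2) and the baseline (SAP 8.4) are all defined. Two things are not settled.
- *Injection type.* SAP 8.2 does not say which patches count. A subject with unchanged rHuPH20 patches and one placebo patch that falls from ++ to + (2 − 1 = 1 grade) qualifies as written.
- *The 48-hour version.* If the SAP 8.4 baseline applies, the change at Day 3 is the Day 3 grade minus itself, which is 0 for every patch. No subject could then qualify, whatever the treatment does.

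**5. Whether a paired summary is feasible.** Each subject has two rHuPH20 and two placebo patches per regimen (Protocol 3.1, SAP 3), and numeric grades exist. One difference per subject, regimen and day follows directly. Neither document gives an SD for it, so the range is an assumption. With SE = SD/√n and n = 20 (√20 = 4.472):
- SD 0.5 grade: 0.5/4.472 = 0.11 grade
- SD 1.0 grade: 1.0/4.472 = 0.22 grade

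These figures only illustrate precision. They do not measure harm from the present wording.

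**The case against.** This is a small pilot that says openly that it is descriptive. Figure 1 puts the labelled patches side by side for each subject, regimen and day, and Listing 8 repeats the scores and marks a maximal score per injection type. For about 20 subjects that is a real, if weak, within-subject comparison. SAP 4 and 9 still require descriptive statistics for all efficacy variables, and nothing says that Appendix A is exhaustive.

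Much of this stands, and it rules out several stronger readings.
- A reader might infer that the missing hypothesis test is the fault. It is disclosed in Protocol Section 8 and in SAP 4 and 9, and it is reasonable in a pilot.
- A reader might infer that the pairing is lost. It is visible in Figure 1 and Listing 8; it is only not quantified.
- A reader might infer that the reduction proportion has no criteria. Grade, threshold and baseline are defined. The injection type is missing, and so is a workable reference at 48 hours.
- A reader might treat Table 6 counts as subjects doing better or worse. They are timing categories and cannot be read that way.
- A reader might infer that no ICDRG statistics will be produced at all. The general promises forbid that conclusion. The accurate charge is that they have no definition or layout behind them.

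The objection does not supply a contrast. A general promise of descriptive statistics does not say how two same-drug patches are combined, and a proportion is a count that should not depend on a qualitative review.

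**Conclusion.** The point holds as a gap between what is declared and what is specified. The primary analysis is named as a paired comparison, but its treatment effect is left to a qualitative review of displays that do not quantify it, and neither regimen has a planned severity summary. One efficacy table out of 15 exists. It covers one regimen, is unpaired and concerns timing. The reduction proportion can be met by a placebo patch, and its 48-hour version is zero by definition if measured from Day 3.

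This should be settled before unblinding. It does not undermine the design or the data, which already support a paired summary. The conclusion rests on the SAP text and layouts. The only assumed quantity is the SD range of 0.5 to 1.0 grade, and the conclusion does not depend on it.

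**What to change.** In SAP 9.1 and Appendix B, add two shells, each for the Evaluable and ITT populations.

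**Paired grade table.** Per subject, regimen and day, take the mean of the two rHuPH20 patches minus the mean of the two placebo patches.
- Regimen 1: use the change from each patch's own Day 3 baseline, at Days 4 to 7 and 14.
- Regimen 2: use the raw grade at Day 3 and at each later day. Note in SAP 8.4 that Day 3 is not a pre-treatment baseline here, because the first injection is given on Day 1.
- Report N, mean, SD, median and range, with counts of subjects lower, equal or higher on rHuPH20.
- Treat an irritant reaction as a missing grade and count these by injection type. If one of two same-drug patches is missing, use the other. If both are missing, omit that subject-day and report how many were omitted. No score is filled in, so SAP 8.5 is respected.

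**Reduction table.** Tabulate a reduction of at least 1 grade from Day 3 in at least one patch, separately for rHuPH20 and placebo patches, as paired counts (both, rHuPH20 only, placebo only, neither) from Day 4 onward. Keep the 48-hour Regimen 2 proportion, but define it as at least one rHuPH20 patch at least 1 grade below the mean of the same subject's placebo patches at Day 3. Show the mirror count for placebo.

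Keep Figure 1 and the medical review alongside these tables.

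**Cost.** SAP wording and two shells in two populations, so 2 × 2 = 4 outputs. No new data are needed. No test or interval is added, so the statement that no formal comparisons are planned still holds. The drawback is that a mean on an ordinal scale with a sponsor-defined 1/2 grade is approximate; the median and the lower/equal/higher counts offset this.
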